7.1 Definitions

Adverse Event

An **adverse event** (AE) is any symptom, sign, illness or experience that develops or worsens in severity during the course of the study. Intercurrent illnesses or injuries will be regarded as adverse events. Abnormal results of diagnostic procedures are considered to be adverse events if the abnormality:

- results in study withdrawal
- is associated with a serious adverse event
- is associated with clinical signs or symptoms
- leads to additional treatment or to further diagnostic tests
- is considered by the investigator to be of clinical significance.

Serious Adverse Event

Adverse events are classified as serious or non-serious. A **serious adverse event** is any AE that is:

CONFIDENTIAL

- fatal
- life-threatening
- requires or prolongs a hospital stay
- results in persistent or significant disability or incapacity
- a congenital anomaly or birth defect
- an important medical event.

Important medical events are those that may not be immediately life threatening, but are clearly of major clinical significance. They may jeopardize the subject, and may require intervention to prevent one of the other serious outcomes noted above. For example, drug overdose or abuse, a seizure that did not result in in-patient hospitalization, or intensive treatment of bronchospasm in an emergency department would typically be considered serious.

All adverse events that do not meet any of the criteria for serious should be regarded as ***non-serious adverse events***.

Adverse Event Reporting Period

The study period during which adverse events must be reported is normally defined as the period from the initiation of any study procedures to the end of the study treatment follow-up. For this study, the study treatment follow-up is defined as 30 days following the last administration of study treatment.

Preexisting Condition

A preexisting condition is one that is present at the start of the study. A preexisting condition will be recorded as an adverse event if the frequency, intensity, or the character of the condition worsens during the study period.

General Physical Examination Findings

At screening, any clinically significant abnormality will be recorded as a preexisting condition. At the end of the study, any new clinically significant findings/abnormalities that meet the definition of an adverse event will also be recorded and documented as an adverse event.

Post-study Adverse Event

All unresolved adverse events will be followed by the investigator until the events are resolved, the subject is lost to follow-up, or the adverse event is otherwise explained. At the last scheduled visit, the investigator will instruct each subject to report any subsequent event(s) that the subject, or the subject's personal physician, believes might reasonably be related to participation in this study.

Abnormal Laboratory Values

A clinical laboratory abnormality should be documented as an adverse event if any one of the following conditions is met:

- The laboratory abnormality is not otherwise refuted by a repeat test to confirm the abnormality.
- The abnormality suggests a disease and/or organ toxicity.

CONFIDENTIAL

- The abnormality is of a degree that requires active management; e.g. change of dose, discontinuation of the drug, more frequent follow-up assessments, further diagnostic investigation, etc.

Hospitalization, Prolonged Hospitalization or Surgery

Any adverse event that results in hospitalization or prolonged hospitalization will be documented and reported as a serious adverse event unless specifically instructed otherwise in this protocol. Any condition responsible for surgery should be documented as an adverse event if the condition meets the criteria for an adverse event.

Neither the condition, hospitalization, prolonged hospitalization, nor surgery are reported as an adverse event in the following circumstances:

- Hospitalization or prolonged hospitalization for diagnostic or elective surgical procedures for a preexisting condition. Surgery should **not** be reported as an outcome of an adverse event if the purpose of the surgery was elective or diagnostic and the outcome was uneventful.
- Hospitalization or prolonged hospitalization required to allow efficacy measurement for the study.
- Hospitalization or prolonged hospitalization for therapy of the target disease of the study, unless it is a worsening or increase in frequency of hospital admissions as judged by the clinical investigator.

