2.1 General Design

This is a single center, double blind randomized cross over design trial that will compare the impact of NAC vs. saline infusion during experimental hypoglycemia on day one on the responses to experimental hypoglycemia on day two. Figure 1 shows the protocol in schematic form. We intend to enroll 18 individuals to obtain the complete data sets from 15 participants.

Expected duration of subject participation is 10-12 weeks. This study will consist of a screening visit and two 2-day intervention visits separated by approximately 8 weeks.

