4.2 Treatment Regimen

A 150 mg/kg loading dose of NAC or saline over the first hour followed by a 50 mg/kg maintenance dose infused over the next 4 hours on days one of both parts of the study.

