7.2 Recording of Adverse Events

At each contact with the subject, the investigator must seek information on adverse events by specific questioning and, as appropriate, by examination. Information on all adverse events will be recorded immediately in the source document, and also in the appropriate adverse event module of the case report form (CRF). All clearly related signs, symptoms, and abnormal diagnostic procedures results will be recorded in the source document, though should be grouped under one diagnosis.

All adverse events occurring during the study period must be recorded. The clinical course of each event will be followed until resolution, stabilization, or until it has been determined that the study treatment or participation is not the cause. Serious adverse events that are still ongoing at the end of the study period must be followed up to determine the final outcome. Any serious adverse event that occurs after the study period and is considered to be possibly related to the study treatment or study participation should be recorded and reported immediately.

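### All adverse events must be recorded for 30 days after the last infusion, but for completers the last scheduled contact is about one day after it

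*Combined protocol and SAP*

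**What the plan says.** **Window.** Section 7.1 runs the reporting period from the first study procedure to the end of treatment follow-up, and "the study treatment follow-up is defined as 30 days following the last administration of study treatment".

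**Scope and method.** Section 7.2: "All adverse events occurring during the study period must be recorded". There is no relatedness condition on this. The method is active: "At each contact with the subject, the investigator must seek information on adverse events by specific questioning".

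**Treatment days.** Section 4.2 places the "maintenance dose infused over the next 4 hours on days one of both parts of the study", so a completer's last administration is on Part 2 Day 1.

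**Contacts.** Section 2.1 gives "a screening visit and two 2-day intervention visits separated by approximately 8 weeks". The last row of the Section 5 visit table is Part 2 Day 2 (clamp and lunch), and no later visit or call is listed. The opening of Section 5 speaks of three-day visits, which conflicts with 2.1 and with the table.

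**After the last visit.** Under the post-study heading of 7.1, "the investigator will instruct each subject to report any subsequent event(s", limited to those that the subject or a personal physician believes may be related to taking part. Events already open are followed until they are resolved, otherwise explained, or the subject is lost to follow-up.

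**Other contact.** Section 3.4.2 plans a call within 1-2 days, only for participants withdrawn because the infusion was stopped early.

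**Duration.** Section 2.1: "Expected duration of subject participation is 10-12 weeks".

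**The concern.** The sponsor chose a 30-day window, all events, and active questioning. The schedule provides no occasion for that questioning after about day 1 of the window. What remains is passive and filtered by relatedness, whereas 7.2 asks for everything. The clamp on Part 2 Day 2 is the last study procedure, and no later contact asks about events that follow it.

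Part 1 is different. A continuing participant comes back about 8 weeks later and can be asked about the whole 30 days after the Part 1 infusion. Events after the Part 2 infusion are therefore less likely to be found. At stake are the completeness of the adverse event tabulation and of the at-least-monthly DSMB review of adverse events in 7.5.

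**Working it through.** The plan gives no figure of its own to reproduce here. The check is schedule arithmetic.

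**Inputs.** Window 30 days (7.1). Infusion on Day 1 of each part (4.2). Last contact Part 2 Day 2 (Section 5 table). Screening about 2-4 days before Day 1 (Section 5). Gap of 8 weeks, or 8±2 weeks for men (Section 5).

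**Days without scheduled contact** = 30 − days from last infusion to last contact.
- Two-day visits: 30 − 1 = 29 of 30 (97%).
- Three-day wording: 30 − 2 = 28 of 30 (93%).

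**Part 1 for comparison.** The next contact is at about day 56 (day 42 to 70 for men). That is after day 30 in every case, so one enquiry at that visit can cover the whole window.

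**Participation** = screening lead + gap + 1 day (to the last visit), or + 30 days (to the end of the window).

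| Gap | To Part 2 Day 2 | To end of 30-day window |
|---|---|---|
| 6 weeks (42 days) | 45-47 days, 6.4-6.7 weeks | 74-76 days, 10.6-10.9 weeks |
| 8 weeks (56 days) | 59-61 days, 8.4-8.7 weeks | 88-90 days, 12.6-12.9 weeks |
| 10 weeks (70 days) | 73-75 days, 10.4-10.7 weeks | 102-104 days, 14.6-14.9 weeks |

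Counting the gap from Part 1 Day 2 adds one day to each entry. At the planned 8-week gap, the stated 10-12 weeks is longer than the time to the last visit and shorter than the time to the end of the window. It is therefore no evidence that a day-30 contact is planned.

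**Does other text close the gap?**
- The 3.4.2 call reaches only participants with an early-stopped infusion, and by day 2 at the latest.
- Following unresolved events covers only those already known.
- The 7.1 self-report covers only events thought related. In 7.2 a relatedness condition appears only for serious events after the study period, so it does not belong inside the 30 days.

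**The case against.** **Practical exposure is small.** Section 1.5 reports that the anaphylactoid reactions tabulated in the package insert all occurred within 2 hours. Treatment is one 5-hour infusion per part in healthy volunteers. The safety endpoint in 2.4 is read at baseline and at 30, 60 and 90 minutes. The boundary in 7.5 counts reactions that stop the infusion. None of these uses days 2-30. This stands, and it limits the weight of the point.

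**The text may be only silent.** The self-report sentence sits under a post-study heading, so it can be read as applying after day 30. The visit table also omits the 3.4.2 call, so a missing row does not prove that no call would be made. This stands in part. On that reading, however, the plan names no method at all for days 2-30, and 7.2 still requires all events.

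**The duration is only an expectation.** At 8 weeks the window ends 4-6 days beyond 12 weeks (88-90 against 84 days), and at 6 weeks it falls inside the stated range. This is fair: the duration is a consequential edit, not the main point.

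**A stronger reading to resist.** A reader might infer that a NAC-versus-saline comparison of adverse events is biased. The documents do not support this. Section 6.2 plans no such comparison. If the two orders are balanced (an assumption, since no allocation ratio is stated), under-recording falls about equally on both treatments. Nor does Part 1 have 8 weeks of active surveillance: it has one recall enquiry at the next visit.

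**Conclusion.** The point holds as a mismatch between a stated safety follow-up and the schedule meant to deliver it. For completers, 28-29 of the 30 required days have no active ascertainment, and nothing is scheduled after the Part 2 Day 2 clamp.

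The consequence is incomplete adverse event tabulation and DSMB review for Part 2 exposures. This affects one exposure per completer, with 15 completers expected from 18 enrolled. A participant who leaves after Part 1 has the same gap after that infusion. The primary efficacy analysis, power, the 2.4 safety endpoint and the 7.5 boundary are untouched, and distortion between treatments is not shown.

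The conclusion assumes that the visit table and 3.4.2 list all planned contacts. It is worth correcting because the plan falls short of its own requirement and the remedy is cheap.

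**What to change.** 1. Add to the Section 5 visit table a telephone contact about 30 days after the last infusion, with the same adverse event questioning as at visits. Include participants who leave after Part 1, if they agree. Section 3.4.2 now ends most data collection at withdrawal, so it needs a matching exception.
2. Make the self-report instruction in 7.1 apply only after that contact.
3. Restate the expected participation in 2.1 and the Study Summary as about 13 weeks with an 8-week gap, or about 11-15 weeks for men at 8±2 weeks.
4. Reconcile the two-day and three-day visit wording, so that the last visit is unambiguous.

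The cost is one short call per participant by existing staff: about 18 calls at the planned enrolment, more if replacements are recruited under 6.1. The stated duration becomes slightly longer. If the sponsor does not want the call, the reporting period in 7.1 has to be matched to the contacts actually planned. That would make the text consistent but would give up the follow-up.

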7.2 Recording of Adverse Events

At each contact with the subject, the investigator must seek information on adverse events by specific questioning and, as appropriate, by examination. Information on all adverse events will be recorded immediately in the source document, and also in the appropriate adverse event module of the case report form (CRF). All clearly related signs, symptoms, and abnormal diagnostic procedures results will be recorded in the source document, though should be grouped under one diagnosis.

All adverse events occurring during the study period must be recorded. The clinical course of each event will be followed until resolution, stabilization, or until it has been determined that the study treatment or participation is not the cause. Serious adverse events that are still ongoing at the end of the study period must be followed up to determine the final outcome. Any serious adverse event that occurs after the study period and is considered to be possibly related to the study treatment or study participation should be recorded and reported immediately.

7.3 Reporting of Serious Adverse Events

7.3.1 Study Sponsor Notification by Investigator

A serious adverse event must be reported to the data safety and monitoring board within 24 hours of finding out of the event using a Serious Adverse Event (SAE) form. The investigator will keep a copy of this SAE form on file at the study site.

CONFIDENTIAL

At the time of the initial report, the following information should be provided:

- Study identifier
- Study Center
- Subject number
- A description of the event
- Date of onset
- Current status
- Whether study treatment was discontinued
- The reason why the event is classified as serious
- Investigator assessment of the association between the event and study treatment

Within the following 48 hours, the investigator must provide further information on the serious adverse event in the form of a written narrative. This should include a copy of the completed Serious Adverse Event form, and any other diagnostic information that will assist the understanding of the event. Significant new information of ongoing serious adverse events should be provided promptly to the data and safety monitoring board.

7.3.2 IRB Notification by Investigator

Reports of all serious adverse events (including follow-up information) must be submitted to the IRB within 10 working days if it falls under the UPIRTSO guidelines. Copies of each report and documentation of IRB notification and receipt will be kept in the Clinical Investigator's binder.

7.3.3 FDA Notification by Sponsor

The study sponsor shall notify the FDA by telephone or by facsimile transmission of any unexpected fatal or life-threatening experience associated with the use of the drug as soon as possible but no later than 7 calendar days from the data and safety monitoring board's original receipt of the information.

If a previous adverse event that was not initially deemed reportable is later found to fit the criteria for reporting, the investigator will submit the adverse event in a written report to the FDA as soon as possible, but no later than 15 calendar days from the time the determination is made.

Agency	Criteria for Reporting	Timeframe	Form to Use	Submission address/fax numbers
U of MN IRB	SAE : fatal, life-threatening or serious, unexpected, at least possibly related	10 working days	UMCC SAE	MMC 820
FDA	SAE : fatal, life-threatening,	7 calendar days	FDA prefers MedWatch	Fax: [name]

CONFIDENTIAL

	unexpected, at least possible related		3500a Form but alternative formats are acceptable (e.g. summary letter)	
	SAE : serious, unexpected, at least possibly related	15 calendar days		

7.4 Unblinding Procedures

Unblinding of participants and investigators will be done at the end of the study and a letter will be sent to any subject withdrawn because of symptoms of an allergic reaction to NAC informing them of the treatment they were given. If they had been given NAC, we will instruct them to share the letter with their personal physician so the allergy could be noted in the clinical record.

7.5 Stopping Rules

Individuals will be withdrawn from the trial if they experience any symptoms of allergy to NAC severe enough to require early stopping of the infusion, including feeling itchy on their skin, having tingling or swelling in their mouth or tongue, or having trouble breathing.

A Data Safety Monitoring Board (DSMB) will be assembled at the start of the study to regularly monitor patient safety and study documentation of adverse and serious adverse events. This board will consist of the study statistician [name], endocrinologist [name] (who is independent of the study team), investigational pharmacist [name], and endocrinologist [name] (who is independent of the study team) from the University of Virginia. DSMB members will be unblinded to treatment assignments. They will review (1) incidence of early stopping of an infusion and (2) incidence of any adverse or serious adverse events on at least a monthly basis. After an experiment where the infusion was stopped early and an adverse or serious adverse event was reported, they will review that experiment's data within two weeks.

Participant accrual will be halted if an excessively high rate of participants with allergic symptoms requiring early stopping of the infusion is seen. Statistical sequential boundaries on the cumulative number of participants with allergic symptoms will be used to monitor the rate. If allergic symptoms requiring early stopping of the infusion are noted during an experiment, the participant will be withdrawn from the trial; the withdrawal will be carried out by blinded study staff, thus without knowledge of whether the infusion given was NAC or saline. The DSMB will then review the unblinded participant data within two weeks of the experiment. If the infusion given was saline, the reaction will be denoted in DSMB records as a placebo reaction, and that participant will not be counted towards the cumulative number of participants with allergic symptoms to NAC. If

CONFIDENTIAL

the infusion given was NAC, and in the DSMB's judgment the reaction was likely related to NAC, then the reaction will be denoted in DSMB records as an allergic reaction to NAC, and that participant will be counted towards the cumulative number of participants with allergic symptoms to NAC. The DSMB will inform the PI that there was an allergic reaction to NAC, and at study's end the project PI will notify the participant that they should inform their personal care provider that an allergic reaction to NAC was observed.

Specifically, the trial will be stopped early if the number of participants with an allergic reaction to NAC is equal to or exceeds the boundary number (bn) out of n participants who have completed at least the Part 1 infusion (Table below). This is a Pocock-type stopping boundary that yields the probability of crossing the boundary at most 0.05 when the rate of allergic symptoms is equal to the acceptable rate of 10%.

Cumulative early stopping rule for allergic symptoms to NAC with 10% as the maximum allowable rate of allergic symptoms.

Number	1	2	3	4	5	6	7	8	9	10	11	12	13	14	15	16	17	18
who have completed at least one Part Boundary,	-	2	3	3	3	3	4	4	4	4	4	4	5	5	5	5	5	6
bn																		

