3.4 Early Withdrawal of Subjects

3.4.1 When and How to Withdraw Subjects

Subjects will be withdrawn at any point during the study if they remove their consent or if they develop any of the exclusion criteria after enrollment. In addition, any subjects who experience the symptoms of an allergic reaction to the NAC severe enough that the infusion is stopped early will be withdrawn from the study at the time the infusion is stopped (before unblinding that participant's treatment assignment). Procedures for withdrawal include collecting the necessary information to provide them with the compensation due them for the time they devoted to the study. At the end of the study, after treatment assignments are unblinded, a letter will be sent to the any subject withdrawn because of symptoms of an allergic reaction to NAC informing them of the treatment they were given. If they had been given NAC, we will instruct them to share the letter with their personal physician so the allergy could be noted in the clinical record.

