3.4.2 Data Collection and Follow-up for Withdrawn Subjects

Data will be collected per the protocol up until the point the subject is withdrawn from the study. No additional data will be collected from subjects after their withdrawal unless they were withdrawn due to early stopping of the infusion. For such participants, a follow-up phone call within 1-2 days will ascertain their status and if hospitalized we will request consent to access hospitalization records. NAC is already used in clinical practice for other indications and it does not have an effect on survival.

CONFIDENTIAL

4 Study Drug

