4.3 Method for Assigning Subjects to Treatment Groups

The investigational pharmacy at the University of Minnesota will be responsible for implementing the randomization order in which participants are given NAC or saline, prepared by the study statistician. This information will be blinded to investigators and participants and they will be unblinded only at the end of the study.

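### A withdrawn participant should be told of a confirmed NAC reaction, and advised to tell a care provider, soon after the DSMB review rather than at study end

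*Combined protocol and SAP*

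**What the plan says.** Section 7.5 has blinded staff withdraw anyone whose infusion is stopped for allergic symptoms. "The DSMB will then review the unblinded participant data within two weeks of the experiment". If the infusion was NAC and the board thinks NAC the probable cause, the case counts towards the stopping boundary and "The DSMB will inform the PI that there was an allergic reaction to NAC". No date is given for that notice. The participant's turn comes at the study's "end the project PI will notify the participant that they should inform their personal care provider".

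Two other sections set the same timing for the participant. Section 3.4.1: "At the end of the study, after treatment assignments are unblinded, a letter will be sent". Section 7.4: "Unblinding of participants and investigators will be done at the end of the study", with a letter asking anyone who had NAC to "share the letter with their personal physician so the allergy could be noted in the clinical record". Section 4.3 says of investigators and participants that "they will be unblinded only at the end of the study".

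Section 3.4.2 governs what follows withdrawal: "No additional data will be collected from subjects after their withdrawal unless they were withdrawn due to early stopping of the infusion". For that group it adds a status call at 1 to 2 days and, if the person is in hospital, a request for consent to see the records. The call is not described as revealing treatment. No section provides for earlier disclosure to the individual.

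**The concern.** The protocol wants a NAC allergy to reach the participant's own clinician and chart; sections 3.4.1, 7.4 and 7.5 all say so. The finding that triggers this is available within two weeks, from a board that knows the assignment. Yet the participant is told at a date set by the rest of the trial's accrual.

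End-of-study unblinding normally protects outcome data still to be collected. Here the person has already left the trial. What is at stake is a period in which someone with a confirmed reaction to a drug in clinical use has neither the confirmation nor the advice to pass it on.

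**Working it through.** **1. What is known, and when**

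| Event | Timing | Section |
|---|---|---|
| Infusion stopped, participant withdrawn by blinded staff | day 0 | 3.4.1, 7.5 |
| Status call | day 1 to 2 | 3.4.2 |
| Unblinded DSMB review and causality judgment | by day 14 | 7.5 |
| DSMB notice to the PI | not dated | 7.5 |
| Participant told it was NAC and advised to inform a care provider | study end | 3.4.1, 7.4, 7.5 |

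The last step needs no information beyond what exists by day 14.

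**2. The stopping boundary is unaffected**

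An exact sequential binomial calculation over n = 1 to 18, with the tabulated boundary and a 10% reaction rate, gives a crossing probability of 0.047. This agrees with the stated limit of 0.05. The reaction is classified and counted at the DSMB review, so telling the participant afterwards changes no figure.

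**3. Length of the wait**

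The documents state neither an accrual period nor a definition of study end. Assume 18 people (section 2.1) enrolled evenly over A months, and study end 8 weeks (1.84 months) after the last person's Part 1. For the k-th person enrolled:

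- reaction in Part 1: wait = A × (18 − k)/17 + 1.84 months
- reaction in Part 2: wait = A × (18 − k)/17 months

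| A (assumed) | k = 1, Part 1 / Part 2 | k = 9, Part 1 / Part 2 | k = 18, Part 1 / Part 2 |
|---|---|---|---|
| 6 months | 7.8 / 6.0 | 5.0 / 3.2 | 1.8 / 0 |
| 12 months | 13.8 / 12.0 | 8.2 / 6.4 | 1.8 / 0 |
| 18 months | 19.8 / 18.0 | 11.4 / 9.5 | 1.8 / 0 |

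The mean over enrolment order and part is A/2 + 0.92, that is 3.9, 6.9 or 9.9 months. Under the fix, notice comes within 2 weeks + 7 days = 3 weeks.

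Section 1.4 gives some context for A. One earlier study enrolled 30 people in 36 months, which scales to 36 × 18/30 = 21.6 months for 18. Another enrolled 11 + 9 + 11 = 31 in 18 months, which scales to 18 × 18/31 = 10.5 months. Both included people with type 1 diabetes, and section 6.3 expects healthy volunteers to be easier to recruit, so these are not forecasts.

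The waits would be shorter if the safety rule stopped the trial early. The k = 18 Part 1 wait would be shorter by A/17 (0.35, 0.71 or 1.06 months) if the study closed with the preceding participant's Part 2. They would be longer if replacements were recruited to reach 15 completers (section 6.1).

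**4. How many people might be affected**

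Section 1.5 cites 180 treated individuals on the planned dosage schedule: 16 with moderate and 2 with severe reactions. For 15 to 18 people exposed to NAC:

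- severe only, 2/180: 0.17 to 0.20 expected; chance of at least one 1 − (178/180)^15 = 15% to 1 − (178/180)^18 = 18%
- moderate or severe, 18/180: 1.5 to 1.8 expected; chance of at least one 1 − 0.9^15 = 79% to 1 − 0.9^18 = 85%

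These are loose proxies. Nothing in the documents says that a moderate reaction would stop an infusion, and the asthma exclusion and diphenhydramine premedication may lower the rates.

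**5. Harm**

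Harm needs re-exposure to NAC before study end, and confirmation (as opposed to suspicion) must change what the clinician does. The documents mention acetaminophen overdose (1.5), intravenous use in neurological-disease research (7.6.1) and clinical use for other indications (3.4.2). They give no rate of re-exposure, so no probability of harm can be computed.

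**The case against.** The timing is a consistent choice: three sections agree on when the participant is told. Much of the information is already in the participant's hands. They felt the symptoms, saw the infusion stop, were withdrawn and get a call within two days. Unresolved events are followed (7.1), and study data may go into medical records (8.2), so a suspected allergy can already be reported. The consent pages were removed, so what participants are told there is unknown. All of this stands, and it limits the size of the point.

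The fix also has a cost to blinding. Section 4.3 gives no randomization method. If small blocks are used (an assumption), one revealed sequence informs others: a known block of 2 fixes the partner's sequence, and in a block of 4 each remaining member's chance of the same sequence falls from 1/2 to 1/3. Calling only confirmed reactors also makes silence informative to other allergy withdrawals, although they too have left the trial. This objection is fair, but using an already unblinded caller largely removes the first problem.

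A reader might go further and infer that the DSMB's notice breaks the PI's blind mid-study and biases the comparison, or that 7.5 contradicts 4.3 and 7.4. The documents do not support either reading. The notice is undated, and it concerns someone who gives no further efficacy data. What remains is a missing date and a missing cross-reference.

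**Conclusion.** The point holds as a modest participant-safety improvement. Confirmation and advice that the protocol itself wants delivered are held back until study end, although the judgment behind them is made within two weeks and the participant has already left the trial. Efficacy data from that person give almost no reason to wait. For a Part 2 reactor, disclosure also reveals that Part 1 was saline, but those samples and scores have been collected by then.

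The wait runs from about zero (the last person enrolled, reacting in Part 2) through 8 weeks (the last enrolled, reacting in Part 1) to many months for early enrollees, all under assumed accrual. At least one affected person is plausible, but the proxy rates are too loose for a firm figure.

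A reader might infer that participants are left unaware of a reaction or exposed to a serious hazard. The documents do not show that: the event is known to the participant, re-exposure of a healthy volunteer is unlikely, and no harm rate is available.

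**What to change.** Change section 7.5, with matching changes in 3.4.1 and 7.4, along these lines:

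> Promptly after the DSMB review (for example within 7 days), or at study end if that is sooner, a participant whose reaction the DSMB attributes to NAC will be told by phone and letter that the infusion was NAC and that they should inform their care provider. An already unblinded person (a DSMB member or the investigational pharmacist) will make the disclosure.

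The 7 days is a suggestion, not a figure derived from the documents. Keep the study-end letter for all other allergy withdrawals. List this disclosure in 4.3 and 7.4 as an exception to end-of-study unblinding. Give the DSMB's notice to the PI a date, and list it as an exception too if it is meant to come before study end.

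The cost is wording in four sections and one call and letter per confirmed reactor. A small risk remains that the participant passes the assignment to blinded staff and so, with small blocks, hints at another participant's sequence. Asking the participant not to discuss it with study staff would reduce that risk.
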